#### **8.1.2. Clinical Laboratory Procedures**

These laboratory evaluations will be conducted primarily at one of the clinical site laboratories available to the research team. Details of specimen collection are found in the Lab Procedures Manual for this study.

At designated visits, the study PI (or designee) assesses the clinical events and the laboratory test results and determines whether the participant can receive VOR doses or HXTC infusions. If values are outside the study reference range, the PI (or designee) determines if the abnormal value is clinically significant and if study treatments can continue. Report all abnormal laboratory values that the investigator deems clinically significant as AEs.

All participants will have safety labs (CBC with differential and chemistries) done throughout the study to monitor for any adverse events due to the administration of VOR and HXTC therapy. Labs that are abnormal and meet grading standards per Division of AIDS (DAIDS) Table for Grading the Severity of Adult and Pediatric Adverse Events, Version 2.1. [July 2017], will be re-assessed based on these initial parameters.

Blood specimens will be collected and evaluated at either UNC McLendon Hospital Lab or LabCorp.

##### **8.1.2.1. HIV -1 Infection Documentation**

##### **8.1.2.2. Donor ID Panel Testing**

The following tests will be performed on samples collected at Step 3, Visit 4. These samples will either be sent to HPC Lab or LabCorp for testing. Test kits, tubes, and sample processing is done in the HPC lab.

- AbO/Rh
- HBsAg
- HB Core antibody
- HIV1/2 plus O
- Syphilis (T. Pallidum IgG)
- HTLV I/II
- CMV total
- HIV-1/HBV/HCV Ulrio NAT
- West Nile Virus NAT
- T. Cruz (Chagas) antibody

##### **8.1.2.3. Clinical Chemistry**

Assessments include Sodium (Na), potassium (K), chloride (Cl), bicarbonate (CO2), glucose, blood urea nitrogen (BUN), creatinine, calcium (Ca), magnesium (Mg), ALT, AST, alkaline phosphatase, total bilirubin.

In addition to the labs listed above, the following labs will be done at screening and Visit 23 only:

- Direct bilirubin will be obtained if participant is on atazanavir.
- Lipase, albumin, total protein, cholesterol, and triglycerides

8.1.2.4. **Hematology** – All assessments include CBC with WBC differential

8.1.2.5. **Safety Labs**

All participants will have safety labs (CBC with differential and chemistries) done at protocol required visits. Labs from the screening visit will be considered baseline. All lab values obtained pre- and post-dosing that are abnormal and meet grading standards per the DAIDS Table for Grading the Severity of Adult and Pediatric Adverse Events, version 2.1, July 2017 will be re-assessed based on these initial parameters.

Creatinine clearance calculations will use the CKD-EPI equation. This calculation can be found at

[https://www.qxmd.com/calculate/calculator\\_251/egfr-using-ckd-epi](https://www.qxmd.com/calculate/calculator_251/egfr-using-ckd-epi)

The creatinine clearance will be required for study enrollment eligibility. The study assesses serum creatinine level at all the safety lab checks and uses the serum creatinine value for toxicity grading and as confirmation to progress to each dosing Step. Grade the serum creatinine per the DAIDS Table for Grading the Severity of Adult and Pediatric Adverse Events, version 2.1, July 2017.

8.1.2.6. **Prothrombin time (PT), INR, and APTT** - at Screening Visit only.

8.1.2.7. **Follicle Stimulating Hormone (FSH) Test**

This test is done at screening to document menopause in women who have been without a period for > 12 months.

8.1.2.8. **HBsAg and Hep C Antibody** Both hepatitis tests must be negative or non-detected to be included on the study. A positive HCV AB test reflexed to Hepatitis C RNA revealing a negative result is acceptable.

8.1.2.9. **RPR**

If positive and participant has documentation of recent appropriate treatment, they may continue in study. Completion of RPR testing occurs again at Step 3, Visit 6 and Step 4, Visit 13.

8.1.2.10. **HIV-1 RNA**

The definition for the HIV-1 RNA quantitative PCR “less than (<) level/limit of detection” or “undetectable per institutional standard” for the purpose of this study will be <50 copies/mL.

8.1.2.11. **CD4+ T cell differential panel**

8.1.2.12. **Serum and Point of Care (POCT) Urine Pregnancy test**

A negative serum pregnancy test (to rule out pregnancy) is required on all women at screening and VOR pre-dose assessment visits, regardless of documented procedures that prohibit pregnancy. The use of the POCT urine pregnancy test as confirmation of negative pregnancy status is acceptable at all visits except screening.

All women regardless of child bearing potential will have a pregnancy test prior to the first VOR dose, prior to the first dose in subsequent series of dosing, as well as at each HXTC infusion. The test must be negative within 48 hours of the dose. Because the study has no direct clinical benefit, this added protection is warranted.

8.1.2.13. **Urinalysis**

Perform this test at Screening and the End of Study Intervention (Visit 23) to establish baseline and evaluate if any changes occurred post therapeutic interventions. Dipstick testing (including protein, glucose, hemoglobin, pH, and ketone) will be done. Microscopic analysis will only be done in the event of abnormal results from dipstick testing.

8.1.3. **Research Laboratory Procedures**

8.1.3.1. **Research analysis to be performed per the SOE**

8.1.3.2. **Immune Response Assay**

Immune responses are assessed using IFNy ELispot response to individual epitopes. Changes in the magnitude of response to any single epitope reflects immune responses induced as a consequence of dosing with VOR-HXTC. T cell phenotype and markers of exhaustion pre and post VOR-HXTC administration will also be evaluated. Tetramer staining and V $\beta$  usage analysis will also be performed in order to track the fate of the infused HXTCs.

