#### **6.2.3. Dosage, Preparation, and Administration of VOR**

The UNC IDS Pharmacy stores, distributes, and maintains accountability for VOR. The dispensing of each dose will be participant specific and by signed prescription. Upon receipt of the VOR doses from IDS, the study coordinator dispenses VOR to the participant in the research clinic according to the dose, schedule, and supportive care guidelines.

Take each VOR dose with food.

The primary IDS pharmacist will be responsible to the principal investigator for maintaining study drug accountability, reconciliation, and record maintenance during the study, including documentation of the amount of study treatments (VOR) received in IDS and the amount administered to each participant.

Participants will be provided their first dose of VOR 400 mg in Step 3, Visit 6 to take 4 in Step 4, Visit 7. Participants will take this dose at home in the morning prior to coming for Visit 7. The study coordinator will provide participants with individualized dosing instructions, clearly identifying the days they are required to take VOR. The study coordinator will contact participants on each dosing day. Participants will be instructed to contact the study coordinator and be prepared to return to the clinic should any adverse event evolve. Participants will be monitored for the development of toxicities. Participants will take the doses approximately 72 hours apart.

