### 7.3.3.1. **Visit 7 (Week 0)**

All female participants require a negative POC urine pregnancy test within 48 hours of Visit 7. If, despite the documentation of infertility, a female participant has a positive pregnancy test at this visit, they will be discontinued from the study and not receive the HXTC infusion or additional doses of VOR.

Estimated Blood Volume: up to 60 ml

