#### 7.3.4.1. Visit 14 – 1st Visit of 2nd series

All female participants will be required to have a negative POC urine pregnancy test within 48 hours of Visit 14. If, despite the documentation of infertility, a female participant has a positive pregnancy test at this visit, she will be discontinued from the study and not receive any additional VOR doses or HXTC infusions.

Estimated Blood Volume: up to 25 mL

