##### 7.3.4.1.2. Pre - 3rd HXTC Infusion

The participant will come to the clinic approximately 3.5 - 4 hours after taking their VOR dose for pre-infusion evaluations.

Reference section 7.3.3.1.2. and SOE for visit procedures and processes.

Documented PI review of clinical labs from Visit 13 as well as review of clinical assessments done at this visit are required prior to the thawing and infusion of HXTC study product.

Note: Administration of HXTC can be delayed up to 1 week pending resolution of physical findings or lab abnormalities.

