## Legend

 CNH product ID will be assigned at this time.

^ Height will be obtained at screening in the CTRC – without shoes.

 Targeted clinical assessments are driven by signs and/or symptoms experienced since the last visit or unresolved signs or symptoms experienced previously and included weight and vital signs (temperature, blood pressure, pulse and respirations).

◊ Clinical labs for screening only include sodium (Na), potassium (K), chloride (Cl), bicarbonate (CO2), glucose, blood urea nitrogen (BUN), creatinine (Cr), calcium (Ca), magnesium (Mg), alanine aminotransferase (ALT), aspartate aminotransferase (AST), alkaline phosphatase (Alk Phos), total bilirubin (total bili). A direct bilirubin will be obtained if participant is on atazanavir. Lipase, albumin, total protein, triglyceride and cholesterol are obtained at screening and Visit 23 only.

 Clinical safety laboratory tests: Na, K, Cl, CO2, Cr, glucose, LT, AST, alk phos, total bili, Ca and Mg.

 Reference Study Specific Lab Manual for collection and processing requirements for research samples.

∞ CBC is required for Apheresis procedures. Labs for UNC can be obtained up to 24 hours prior to visit or STAT on the day of the procedure. The CBC for the American Red Cross or other local blood collection agency will be drawn per facility requirement up to 30 days prior to the collection.

 POCT pregnancy testing will be done on all women prior to initiation of VOR and at all HXTC infusions.

 Draw 25.5 mL (3 – 8.5 mL ACD tubes) at these selected time points.

↳ Samples come from the leukapheresis product and are sent to [name] Lab at UNC ambient for processing.

(T) Participants will be contacted via agreed upon communication mechanism to assess for adverse events.

 Labs may be obtained up to 48 hours prior to visit.

 Draw labs STAT, if done on day of visit. Results must be obtained and reviewed prior to procedure or infusion.

 If enrollment occurs on the day of the baseline leukapheresis, draw these samples on Visits 5 and 6, as indicated on the SOE.

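### The pregnancy test required before VOR doses 1 and 11 is tied to Visits 7 and 14, so a same-day test can follow the home dose by about 3.5-4 hours or more

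*Combined protocol and SAP*

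**What the plan says.** **The rule.** Section 8.1.2.12 states: "All women regardless of child bearing potential will have a pregnancy test prior to the first VOR dose". It applies the same requirement to the first dose of each later series and to every HXTC infusion, and adds: "The test must be negative within 48 hours of the dose". SOE legend 5 repeats the order: "POCT pregnancy testing will be done on all women prior to initiation of VOR and at all HXTC infusions". With two series of ten doses, the VOR doses concerned are 1 and 11.

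**The visit instructions.** For Visit 7, section 7.3.3.1 says: "All female participants require a negative POC urine pregnancy test within 48 hours of Visit 7". For Visit 14, section 7.3.4.1 says: "All female participants will be required to have a negative POC urine pregnancy test within 48 hours of Visit 14". Neither says that the test must come before that morning's VOR dose. Both say that a positive test at the visit means discontinuation, with no infusion and no additional VOR.

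**The SOE.** The Visit 14 urine test carries legends 7 and 8. Legend 7 permits collection up to 48 hours before the visit. Legend 8 permits a STAT test on the day, with this condition: "Results must be obtained and reviewed prior to procedure or infusion".

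**When VOR is taken.** On dose 1, section 6.2.3 says: "Participants will take this dose at home in the morning prior to coming for Visit 7". Dose 11 is handed out at Visit 13 to take home (7.3.3.7) and taken on the morning of Visit 14 (7.3.4.1.1). On arrival at Visit 14, section 7.3.4.1.2 says: "The participant will come to the clinic approximately 3.5 - 4 hours after taking their VOR dose for pre-infusion evaluations". Section 7.3.3.1.2 gives the same interval for Visit 7.

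**The concern.** The general rule takes the VOR dose as its reference point. The visit sections take the visit, and legend 8 takes the infusion. These would be equivalent if VOR were given in clinic after the test, but it is taken at home hours before arrival. A site that follows 7.3.4.1 and legend 8 to the letter can therefore breach 8.1.2.12. On that path the test still protects against the infusion and all later treatment, but not against the VOR dose it was meant to precede.

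Section 8.1.2.12 justifies testing every woman, whatever her documented fertility status, on the ground that the study offers no direct clinical benefit. Section 2.2.7 reports that VOR crossed the placenta in rats and rabbits, that in vitro genetic toxicity assays were positive, and that there are no human safety data in pregnancy. What is at stake is one avoidable 400 mg exposure before a positive result is known. No endpoint or analysis is affected.

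**Working it through.** The plan gives no figure to reproduce. The check compares the reference points and then does the arithmetic on the visit windows.

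**1. Reference points**

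| Source | Test is timed against | Must it precede VOR? |
|---|---|---|
| 8.1.2.12 | VOR dose, 48 hours | Yes |
| SOE legend 5 | Start of VOR; each infusion | Yes |
| 7.3.3.1 | Visit 7, 48 hours | Not stated |
| 7.3.4.1 | Visit 14, 48 hours | Not stated |
| SOE legend 7 (marked at Visit 14) | Up to 48 hours before the visit | Optional early route |
| SOE legend 8 (marked at Visit 14) | Procedure or infusion | No |

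**2. Same-day path**

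- Dose taken at home: time 0.
- Arrival in clinic: 3.5 to 4 hours (7.3.3.1.2, 7.3.4.1.2).
- Earliest on-site test: 3.5 to 4 hours after the dose.
- Infusion: about 6 hours after the dose (7.3.3.1.1).

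A result between arrival and infusion satisfies legend 8 and the visit section, but comes after the VOR dose.

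**3. Do the earlier pregnancy tests close the gap?** The pre-dose criteria at Visits 6 and 13 include a negative serum pregnancy test.

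*Dose 1.* Visit 6 may be up to 21 days before Visit 7 (7.3.2.2). It meets the 48-hour limit only if it happens to be scheduled within 2 days of Visit 7, which nothing requires.

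*Dose 11.*
- Visit 13 = Visit 12 + 7 to 14 days (7.3.3.7).
- Visit 14 = about Visit 12 + 28 to 35 days (section 4.5, 4-5 weeks after dose 10).
- Shortest gap: 28 − 14 = 14 days.
- Longest gap: 35 − 7 = 28 days, capped at 21 days by 7.3.3.7 and the Step 5 window table.
- The Visit 13 test is therefore 14-21 days old at dose 11, against a limit of 2 days. The SOE places Visits 13 and 14 at weeks 6 and 8, which also gives 14 days.

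For the Visit 13 test to count, Visit 14 would have to fall no later than 14 + 2 = 16 days after Visit 12, well short of the planned 28. On the planned schedule it cannot satisfy the rule.

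**4. Other checks before the dose.** The contact that confirms when to take dose 1 or 11 depends on acceptable Visit 6 or Visit 13 labs, not on a 48-hour pregnancy test (7.3.2.2, 7.3.3.7). The documented PI review at Visits 7 and 14 must precede thawing and infusion of HXTC, not the VOR dose (7.3.3.1.2, 7.3.4.1.2).

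**5. Extent.** Doses 1 and 11 are 2 of 20. A positive same-day test at Visit 7 still prevents 20 − 1 = 19 VOR doses and all five infusions. At Visit 14 it prevents 20 − 11 = 9 doses and three infusions.

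**The case against.** The strongest reply is that nothing is missing. The order is stated in both 8.1.2.12 and legend 5, legend 7 supplies a route that satisfies every section, and legend 8 is a general laboratory footnote, also used for blood counts and chemistries, that does not claim to override 8.1.2.12. A negative pregnancy test is already among the pre-dose criteria at Visits 6 and 13, so what remains is how recent the test is. A positive result at the visit stops all further treatment. And women enter only with documented hysterectomy, bilateral oophorectomy, tubal ligation or other permanent sterilization, or FSH-confirmed menopause (5.1.12, 5.2.2).

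Much of this stands. An earlier negative test does precede each series, exposure before a stop is limited to one dose, and the consequence is very small. Evidence for Visit 7 is also thinner: the Step 4 columns of the SOE are blank in the copy reviewed, so the legend 8 mark is confirmed for Visit 14 only, and at Visit 7 the point rests on the silence of 7.3.3.1. The laboratory manual was not available.

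It does not remove the conflict. The sponsor chose a 48-hour limit with full knowledge of the infertility criteria, and a test two to three weeks old does not meet it. Legend 7 is only an option, and no visit instruction makes it mandatory before the dose.

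**Conclusion.** The concern holds as a minor internal conflict in a safety procedure. For VOR doses 1 and 11, the visit sections allow a pregnancy test timed to the visit, and the SOE at Visit 14 expressly allows a same-day result due only before the infusion. Done on site that day, the test follows the dose by about 3.5-4 hours or more and cannot satisfy 8.1.2.12.

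The conclusion assumes that same-day tests are done in clinic, that participants arrive when the protocol says, and that Visit 14 falls roughly 4-5 weeks after dose 10. The documents do not give the number of women among the 12 participants, so no count of affected participants can be given.

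**What to change.** - In 7.3.3.1 and 7.3.4.1, require a negative pregnancy test resulted within the 48 hours before VOR doses 1 and 11, and confirmed before the participant is told to take the dose. This makes the existing legend 7 option mandatory at these two points.
- In the SOE, remove legend 8 from the Visit 14 urine pregnancy test, and from Visit 7 if it is marked there.
- Leave the same-day option for the pregnancy test at Visits 10, 16 and 19, where the test governs the infusion.

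A bare cross-reference to 8.1.2.12 in the two visit sections would be lighter, but would leave the same-day permission standing in the SOE.

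The cost is protocol and SOE wording. No test is added; some women may need a separate test visit in the 48 hours before Visits 7 and 14.

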**8.1.3.3. Stored Plasma for Single Copy Assay**

Plasma for HIV-1 RNA SCA will be obtained as required per the SOE and stored for batched analyses. PBMCs will be processed off these samples and stored for future study analysis.

**8.1.3.4. PBMCs for HDAC Responsive Gene Measurement**

PBMCs will be used to confirm pharmacologic effect of VOR on cellular targets *in vivo*. We will isolate total RNA from PBMCs and evaluate the expression of several genes with predictable behavior in response to HDAC inhibition *in vitro* and *in vivo*.

**8.1.3.5. Limiting Dilution Cultures of Resting CD4+ T Cells to Quantify Resting Cell Infection**

Lymphocytes are obtained by continuous-flow leukapheresis and resting CD4 positive T-cells are isolated as previously described [51]. A maximum likelihood method will be used to calculate the infectious units per million of resting CD4+ T-cells. Exploratory assays for quantitation of resting cell infection may include digital droplet PCR of resting cell associated RNA.

**8.1.3.6. Clinical Pharmacokinetics**

We will collect a PK sample at designated time points throughout the study. Please reference SOE for exact time points.

**8.1.3.7. Ex-vivo Latent Clearance Assay**

Resting CD4 cells are isolated via negative selection from a leukapheresis product and then activated. After 15 days of culture, each well is assessed for the presence of residual HIV infection with an HIV-1 gag p24 ELISA performed on supernatant.

**8.1.3.8. Epitope Mapping**

If sufficient cells are available we will perform Epitope mapping of the HXTC product and compare circulating HIV-1 reactive T cell frequencies pre- and post- VOR administration and HXTC infusions. We will also conduct mapping of individual HIV-1 reactivated T cell epitopes targeted by T cell populations and their dominance hierarchies pre- and post-administration of VOR doses and HXTC infusions in Steps 4 and 5.

**8.1.3.9. HLA Typing**

HLA typing is performed on participant peripheral blood at the time of blood collection for HXTC manufacture. For product release, HLA typing will also be performed on the final product to confirm identity. In addition, HLA typing results will be used to inform epitope specific responses as part of the HXTC product characterization.

#### **8.1.3.10. Specimen Preparation, Handling, and Shipping**

Specimen processing and shipment will follow the Study SOPs and Lab Procedures Manual.

#### **8.1.4. Sample Storage**

Participants sign a separate consent for the use and storage of these blood samples for research analysis associated with this study. The research analysis includes genetic testing, and this information will be included in the blood storage consent reviewed with the participants. Participants can opt out of genetic testing.

Any remaining specimens that will be stored for future research will be stored safely and securely in a research specimen storage laboratory at the University of North Carolina at Chapel Hill (UNC-CH). No protected health information (PHI) is included with the samples. All samples are identified by coded number only.

The link between Participant Identifier Code on the samples and PHI is maintained in a secured file on a secured server in the control of the principal investigator at UNC-CH. Future researchers would not have access to this link. Only study personnel, people who work at the research specimen storage laboratory at UNC-CH and IRB approved researchers will have access to the participants' samples. Since all the stored specimens are de-identified, the people who work at the research specimen storage laboratory will not have any personally identifying information that would link to a participant. The IRB approved researchers who receive the specimens may receive information pertaining to lab assay values, age, and sex of the specimen donor, but will not be given the name or any other information that identifies the donor/participant. These samples will be stored indefinitely.

### **9. CLINICAL MANAGEMENT ISSUES**

Criteria for participant management, treatment interruption, and study discontinuation will be mandated only for toxicities possibly, probably, or definitely related to HXTC and/or VOR.

NOTE: In the event that a participant develops toxicity related to his/her previously-stable ART, consultation with the protocol team will be required (preferably before appropriate therapy modification). Toxicities due to drugs in the antiretroviral regimen should be managed according to standard clinical practice, with the goal of maintaining continuous therapy, if possible.

AEs assessed as related to non-study drugs (concomitant medications) should be handled according to the relevant package inserts and the best medical judgment of the site investigator or designee.

Infusion site reactions will be graded according to the DAIDS toxicity grading table.

U.S. Department of Health and Human Services, National Institutes of Health, National Institute of Allergy and Infectious Diseases, Division of AIDS. Division of AIDS (DAIDS) Table for Grading the Severity of Adult and Pediatric Adverse Events, Version 2.1. [July 2017], which is available on the DAIDS RSC website.

